8.3.2. Method of Detecting AEs and SAEs

Care will be taken not to introduce bias when detecting AEs and/or SAEs. Open-ended and nonleading verbal questioning of the participant is the preferred method to inquire about AE occurrences.

8.3.3. Follow-up of AEs and SAEs

After the initial AE/SAE report, the investigator is required to proactively follow each participant at subsequent visits/contacts. All SAEs [and AEs of special interest (as defined in Section 8.3.9)] will be followed until resolution, stabilization, the event is otherwise explained, or the participant is lost to follow-up (as defined in Section 7.3).

The investigator is obligated to perform or arrange for the conduct of supplemental measurements and/or evaluations as medically indicated or as requested by the sponsor or designee to elucidate the nature and/or causality of the AE or SAE as fully as possible. This may include additional laboratory tests or investigations, histopathological examinations, or consultation with other health care professionals.

If a participant dies during participation in the study or during a recognized follow-up period, the investigator will provide the sponsor or designee with a copy of any postmortem findings including histopathology.

New or updated information will be recorded in the originally completed eCRF.

The investigator will submit any updated SAE data to sponsor or designee within 24 hours of receipt of the information.

8.3.4. Regulatory Reporting Requirements for SAEs

- Prompt notification by the investigator to the sponsor of an SAE is essential so that legal obligations and ethical responsibilities towards the safety of participants and the safety of a study intervention under clinical investigation are met.
- The sponsor has a legal responsibility to notify both the local regulatory authority and other regulatory agencies about the safety of a study intervention under clinical investigation. The sponsor will comply with country-specific regulatory requirements relating to safety reporting to the regulatory authority, IRBs/IECs, and investigators.

- An investigator who receives an investigator safety report describing an SAE or other specific safety information (eg, summary or listing of SAEs) from the sponsor will review and then file it along with the investigator's brochure and will notify the IRB/IEC, if appropriate according to local requirements.
- Investigator safety reports must be prepared for SUSARs according to local regulatory requirements and sponsor policy and forwarded to investigators as necessary.

8.3.5. Adverse Reactions, Serious Adverse Reactions, and Suspected Unexpected Serious Adverse Reactions – Expedited reporting within the EU

For the purposes of expedited reporting within the EU, the Sponsor will follow the applicable definitions for ARs, SARs, and SUSARs (for example, as outlined in Article 2 [n,o,p] of Directive 2001/20/EC). Also, seriousness criteria for AEs/ARs (as would apply to SARs and SUSARs) are currently included in the protocol, listed in Section 10.3, Appendix 3.

Adverse Reaction: all untoward and unintended responses to an investigational medicinal product related to any dose administered.

Serious Adverse Reaction: an adverse reaction that results in death, is life-threatening, requires hospitalisation or prolongation of existing hospitalisation, results in persistent or significant disability or incapacity, or is a congenital anomaly or birth defect (see Section 10.3, Appendix 3 for further details pertaining to seriousness criteria).

Suspected Unexpected Serious Adverse Reaction: a serious adverse reaction, the nature or severity of which is not consistent with the applicable product information (eg, the investigator's brochure).

8.3.6. Pregnancy

- Details of all pregnancies in female participants and female partners of male participants will be collected after the start of study intervention and until the Follow-Up Visit (Visit 8) or 30 days after the last dose of study intervention if the Follow-Up Visit is not done.
- If a pregnancy is reported, the investigator should inform the sponsor or designee within 24 hours of learning of the pregnancy and should follow the procedures outlined in Section 10.7 (Appendix 7).
- Abnormal pregnancy outcomes (eg, spontaneous abortion, fetal death, stillbirth, congenital anomalies, ectopic pregnancy) or genetic abnormalities (whether leading to an elective abortion or not) are considered SAEs.

8.3.7. Disease-related Events and/or Disease-related Outcomes Not Qualifying as AEs or SAEs

Signs and symptoms associated with acute migraine attack, eg, aura symptoms, headache pain, nausea and vomiting, sensitivity to light or sound, are considered to be manifestations of migraine and will be captured in the eDiary as symptoms of the disease but they will not be reported as AEs, unless they change in severity or frequency, when they are to be considered as AE. If those events meet SAE criteria, they need to be reported as AEs and SAEs as appropriate. If the investigator considers these manifestations to have a reasonable possibility of relationship to the study intervention(s), then they should be reported as AEs or SAEs, respectively. Please also see Section 10.3 (Appendix 3).

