10.3. Appendix 3: Adverse Events: Definitions and Procedures for Recording, Evaluating, Follow-up, and Reporting

Definition of AE

AE Definition

 An AE is any untoward medical occurrence in a patient or clinical study participant, temporally associated with the use of study intervention, whether or not considered related to the study intervention. An AE can therefore be any unfavorable and unintended sign (including an abnormal laboratory finding), symptom, or disease (new or exacerbated) temporally associated with the use of study intervention. 
AE of Special Interest
 
An adverse event of special interest (serious or nonserious) is one of scientific and medical concern specific to the sponsor’s study intervention or program, which warrants ongoing monitoring and rapid communication by the investigator to the sponsor. Such an event might warrant further investigation in order to characterize and understand it.
 
The following AESI(s) have been identified for the study intervention(s) in this protocol:
 
 Treatment-emergent suicidal ideations with intent, with or without a plan, (ie, Type 4 or 5 on the C-SSRS) or any suicidal behaviors. Treatment-emergent elevated ALT or AST laboratory value $\geq 3 \times$ ULN. Potential Hy’s law cases: elevated ALT or AST laboratory value that is $\geq 3 \times$ ULN and an elevated total bilirubin laboratory value that is $\geq 2 \times$ ULN and, at the same time, an alkaline phosphatase laboratory value that is $< 2 \times$ ULN.

Participants with any AESI(s) will be closely monitored. Selected nonserious and serious adverse events are of special interest and will require immediate reporting, recording, and follow-up.

Reporting requirements for ALT or AST elevations and potential Hy's law cases are outlined in Section 10.3.1. and 10.3.2. below. Responses to the C-SSRS that meet the above criterion will be captured in the eTablet and monitored by the sponsor. These AEs or events determined to be SAEs must be reported appropriately via the designated eCRFs and safety forms.

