 - The test result requires additional diagnostic testing or medical/surgical intervention, and/or
 - The test result leads to a change in study dosing (outside of any protocol-specified dose adjustments) or discontinuation from the study, significant additional concomitant drug treatment, or other therapy, and/or
 - The test result is considered to be an AE by the investigator or sponsor.
- Exacerbation of a chronic or intermittent pre-existing condition including either an increase in frequency and/or intensity of the condition
- New condition detected or diagnosed after study intervention administration even though it may have been present before the start of the study
- Signs, symptoms, or the clinical sequelae of a suspected drug-drug interaction
- Signs, symptoms, or the clinical sequelae of a suspected overdose of either study intervention or a concomitant medication. Overdose per se will not be reported as an AE or SAE unless it is an intentional overdose taken with possible suicidal/ self-harming intent. Such overdoses should be reported regardless of sequelae.
- Lack of efficacy or failure of expected pharmacological action per se will not be reported as an AE or SAE. Such instances will be captured in the efficacy assessments. However, the signs, symptoms, and/or clinical sequelae resulting from lack of efficacy will be reported as AEs or SAEs if they fulfil the definition of an AE or SAE.

Events NOT Meeting the AE Definition

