
 • Any clinically significant abnormal laboratory findings or other abnormal safety assessments that are associated with the underlying disease, unless judged by the investigator to be more severe than expected for the participant’s condition. Merely repeating an abnormal test, in the absence of any of the above conditions, does not constitute an AE. Any abnormal test result that is determined to be an error does not require recording as an AE. • The disease/disorder being studied or expected progression, signs, or symptoms (clearly defined) of the disease/disorder being studied, unless more severe than expected for the participant’s condition • The following events are considered to be manifestations of migraine and will be captured in the eDiary as symptoms of the disease but they will not be reported as AEs, unless they change in severity or frequency warranting an AE, or meet criteria of SAE: 
 • Signs and symptoms associated with acute migraine attack, eg, aura symptoms, headache pain, nausea and vomiting, sensitivity to light or sound. 
If the investigator considers these manifestations to have a reasonable possibility of relationship to the study intervention(s), then they should be reported as AEs or SAEs, respectively.
 • Medical or surgical procedure (eg, endoscopy, appendectomy): the condition that leads to the procedure is the AE • Situations in which an untoward medical occurrence did not occur (social and/or convenience admission to a hospital) • Anticipated day-to-day fluctuations of pre-existing disease(s) or condition(s) present or detected at the start of the study that do not worsen

Definition of SAE

SAEs must meet both the AE criteria described above and the seriousness criteria listed below.

An SAE is defined as any untoward medical occurrence that, at any dose:

a. Results in death

b. Is life threatening
 
The term life threatening in the definition of serious refers to an event in which the participant was at risk of death at the time of the event. It does not refer to an event that hypothetically might have caused death if it were more severe.

c. Requires inpatient hospitalization or prolongation of existing hospitalization

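### Protocol Section 8.3.7 and Appendix 3 give conflicting rules on when migraine symptoms become AEs, so worsening migraine can enter the overall TEAE rate, more often on placebo (minor)

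*Protocol*

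**What the plan says.** Protocol 8.3.7 treats aura, headache pain, nausea, vomiting and sensitivity to light or sound as manifestations of migraine to be captured in the eDiary. It then says that "they will not be reported as AEs, unless they change in severity or frequency, when they are to be considered as AE". Events that are serious, or that the investigator considers possibly related to study intervention, are reportable as well. The section ends by sending the reader on: "Please also see Section 10.3 (Appendix 3").

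Appendix 3 (Section 10.3) bears on the same event in several places:

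- The AE definition: "An AE is any untoward medical occurrence in a patient or clinical study participant".
- Under events that meet the AE definition: "Exacerbation of a chronic or intermittent pre-existing condition including either an increase in frequency and/or intensity of the condition".
- In the same list: "Lack of efficacy or failure of expected pharmacological action per se will not be reported as an AE or SAE". Such instances go to the efficacy assessments, but signs, symptoms and "clinical sequelae resulting from lack of efficacy will be reported as AEs or SAEs if they fulfil the definition of an AE or SAE".
- Under events that do not meet the definition: "The disease/disorder being studied or expected progression, signs, or symptoms (clearly defined) of the disease/disorder being studied, unless more severe than expected".
- In that list again, for migraine specifically, symptoms are not AEs "unless they change in severity or frequency warranting an AE, or meet criteria of SAE".

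On analysis, SAP 10.2.1 summarises TEAEs overall and by system organ class (SOC) and preferred term. SAP 10.2.3 adds tables by relationship, by severity and for common terms. No planned summary leaves out migraine or headache terms.

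**The concern.** Change in migraine frequency is the primary endpoint. If a site applies 8.3.7 as written, a participant whose migraine gets worse has an AE because the efficacy outcome moved. Atogepant is expected to reduce migraine days, so such AEs should arise more often on placebo. The overall TEAE percentage would then partly measure efficacy, in the direction that flatters atogepant. How far it does so would depend on which sentence each of about 125 sites followed. No planned table lets a reader see the overall rate without these events.

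**Working it through.** **The rules side by side.** Take a participant with two more migraine days in one month than at baseline, with attacks of the usual severity.

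| Rule | Is it an AE? |
|---|---|
| 8.3.7 | Yes: frequency changed |
| Appendix 3, exacerbation item | Yes, if regarded as an exacerbation, since frequency increased |
| Appendix 3, migraine item | Only if the change warrants an AE, a test that is not defined |
| Appendix 3, disease-under-study item | No, unless more severe than expected |
| Appendix 3, lack-of-efficacy item | Not per se; its signs, symptoms and sequelae are if they meet the AE definition |

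The items do not give one answer, and 8.3.7 lacks the qualifier in the migraine item of the appendix it cites.

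**No plan figure to reproduce.** The documents give no expected TEAE rate, and nothing on what share of worsenings would be recorded. What follows is an illustration.

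**Inputs.**
- Mean change in monthly migraine days in the completed Phase 3 study (Protocol 2.2): -2.48 on placebo, -4.20 on atogepant 60 mg QD.
- SD of change (Protocol 9.2 and Table 9-3): 3.00 in that study, 3.5 for planning, 4.6 at month 3 in the cited treatment-failure study. As a check on 3.5: 150 × 0.85 = 127.5 per arm gives power of about 97% at -1.7 and 95% at -1.6, as stated.
- Assumed: normal changes; other TEAEs independent of worsening; other-TEAE rate on placebo r = 30% to 60%; share of worsenings recorded as AEs f = 10% to 100%.

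**Step 1: who worsens.** P(change > 0) = Φ(mean/SD).

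| SD | Placebo | Atogepant | Gap (points) |
|---|---|---|---|
| 3.0 | Φ(-0.827) = 20.4% | Φ(-1.400) = 8.1% | 12.3 |
| 3.5 | Φ(-0.709) = 23.9% | Φ(-1.200) = 11.5% | 12.4 |
| 4.6 | Φ(-0.539) = 29.5% | Φ(-0.913) = 18.1% | 11.4 |

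At SD 3.5 this is about 36 and 17 of 150.

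**Step 2: what the overall rate could conceal.** With worsening rates q_P and q_A, the overall TEAE rate on placebo is 1 - (1 - r)(1 - f·q_P). The atogepant excess in other TEAEs that would leave the two overall rates equal is

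(1 - r) · f · (q_P - q_A) / (1 - f·q_A).

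At SD 3.5, f = 1 and r = 0.30: 0.70 × 0.124 / 0.885 = 9.8 points. With r = 0.60: 0.40 × 0.124 / 0.885 = 5.6 points.

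| Share recorded (f) | Excess concealed, r from 60% down to 30% |
|---|---|
| 10% | 0.5 to 0.9 points |
| 25% | 1.3 to 2.2 points |
| 50% | 2.6 to 4.6 points |
| 100% | 5.6 to 9.8 points |

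**The case against.** The strongest answer is that 8.3.7 should not be read alone. It cites Appendix 3, where an AE must be untoward, the change must warrant an AE, disease symptoms must be more severe than expected, and lack of efficacy is not an AE per se. Day-to-day fluctuation that does not worsen is also excluded there. This stands against a stronger reading that a reader might infer, namely that any change, improvement included, is an AE. That reading would also reverse the direction. At SD 3.5, a change of at least one day either way occurs in about 82% on placebo, Φ(1.48/3.5) + Φ(-3.48/3.5), and about 89% on atogepant, Φ(3.20/3.5) + Φ(-5.20/3.5). The placebo excess holds for worsening only. The answer does not remove the conflict, because the exacerbation item in the same appendix points back towards 8.3.7.

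Second, full recording is unrealistic. AEs are elicited by open, non-leading questions (Protocol 8.3.2), not derived from diary counts, and the model counts even a fractional rise as worsening. This stands, so the last row of the table is a ceiling.

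Third, a reader might infer that the rule could hide an atogepant safety signal. Other events keep their own preferred-term rows, and serious events, discontinuations and AESIs are reported separately. What remains is dilution of the overall rate and of SOC totals containing these terms. Nausea or vomiting recorded under its own term would blur that row too, although Appendix 3 asks for the diagnosis rather than the symptoms whenever possible.

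Fourth, recording worsening as an AE is the inclusive choice, and a narrow rule carries a safety cost. This also stands, and the fix should not drop suspected drug-related worsening.

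**Conclusion.** The concern holds as a minor one. Section 8.3.7 and Appendix 3 conflict. Where 8.3.7 is followed alone, worsening of the efficacy outcome can be recorded as a TEAE, and this is expected more often on placebo. The effect is confined to the overall TEAE rate and the SOC totals that contain these terms. Its size cannot be fixed from the documents. The range from under 1 point to a ceiling of 9.8 points rests on assumed TEAE rates, assumed recording shares, normality, independence, and means carried over from the earlier study. None of these figures is an estimate for this trial. The documents do not support a claim that an excess in a specific adverse event would be concealed.

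**What to change.** **Protocol 8.3.7 and Appendix 3.** State one rule in both places, using wording already in Appendix 3. Refer to worsening rather than *change*, and say what *warranting an AE* means and against which reference period. State that lack of efficacy shown only by eDiary counts belongs to the efficacy assessments. Keep events that are serious, or suspected to be related to study intervention, reportable.

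**SAP 10.2.2.** Add one overview row: any TEAE excluding migraine and headache preferred terms, shown beside the overall TEAE figure planned in 10.2.1. As printed, the 10.2.2 list names serious TEAEs twice and has no any-TEAE row, so print both figures there.

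**Cost.** A short wording change with a site note, and one extra table row. Mild worsening seen only in the eDiary would be reported as efficacy data only. SAP version 2.0 already describes regional enrolment in the past tense, so new protocol wording may come too late for AEs already recorded. The SAP row works either way, but it does not remove migraine-related nausea or vomiting coded under its own term.

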8.3.8. Protocol-specific AEs

Not applicable.

8.3.9. AEs of Special Interest

AEs of special interest that warrant ongoing monitoring and rapid communication by the investigator to the sponsor are outlined and specific liver safety guidelines to be followed for this protocol are outlined in Section 10.3 (Appendix 3).

8.3.10. Medication Errors

Medication error refers to any unintended error in the dosing and/or administration of the study intervention as per instructions in the protocol. Medication errors generally fall into 4 categories as follows:

- Wrong study drug
- Wrong dose (including dosing regimen, strength, form, concentration, amount)
- Wrong route of administration, including wrong site of administration (eg, wrong eye)
- Wrong participant (ie, not administered to the intended participant)

Medication errors include occurrences of overdose and underdose of the study intervention.

Overdose: Unintentional administration of a quantity of the study intervention given per administration or per day that is above the maximum recommended dose according to the reference safety information or protocol for the study intervention or comparator as applicable. This also takes into account cumulative effects due to overdose.

An overdose is any unintentional administration of atogepant above 60 mg per day as per the protocol.

Underdose: Unintentional administration of a quantity of the study intervention given per administration or per day that is under the minimum recommended dose according to the reference safety information or protocol.

8.4. Treatment of Overdose

For this study, any dose of atogepant greater than 60 mg within a 24-hour time period will be considered an overdose.

At present, specific information regarding treatment of overdose of atogepant is not available. In case of an overdose, it may be considered that the stomach be emptied and oral gavage with activated charcoal be used to help reduce absorption of atogepant.

In the event of an overdose, the investigator/treating physician should:

1. Contact the medical safety physician immediately.
2. Closely monitor the participant for any AE/SAE and laboratory abnormalities until atogepant can no longer be detected systemically (at least 2 days).
3. Obtain a plasma sample for PK analysis within 2 days from the date of the last dose of study intervention if requested by the medical safety physician (determined on a case-by-case basis).
4. Document the quantity of the excess dose as well as the duration of the overdose in the eCRF.

Decisions regarding dose interruptions or modifications will be made by the investigator in consultation with the medical safety physician based on the clinical evaluation of the participant.

8.5. Pharmacokinetics

8.5.1. Blood PK Sampling Procedure

A blood sample for PK analysis will be collected on site at Visits 2, 3, 4, 5, 6, and 7/ET from participants who consent to participate in the PK substudy. Participants can withdraw consent to participate in the PK substudy at any time and should have no further PK samples collected. Each participant in the PK substudy will be asked to provide a total of 6 blood samples (1 per visit). At Visit 2, the sample should be collected prior to the initial dose of study intervention taken at the clinic. During one of the Visits 3 to 6, the sample should be collected prior to the daily dose of study intervention (participant should wait to take the dose in the clinic after PK sample collection), and the samples collected at the remaining visits should be collected 1 to 10 hours post the daily dose. At Visit 7 the sample should be collected 1 to 10 hours post the daily dose.

The date and time of collection of each PK sample will be recorded in the eCRF. In addition, for each of the PK samples collected (except the Visit 2 sample) the date and time of taking study intervention prior to the PK sample should be recorded. PK samples will be collected, stored (frozen), and shipped according to instructions provided in the laboratory manual.

The treatment codes will be provided to the bioanalytical lab using a secure process, ensuring no one outside the bioanalytical team is unblinded, to allow only atogepant-treated participant PK samples to be analyzed. The bioanalytical method for the determination of individual plasma concentrations of atogepant and the performance of the assay during validation and sample analysis will be summarized in a separate bioanalytical report, including the results obtained

from analysis of the PK samples. The bioanalytical report will be appended to the integrated clinical trial report.

Drug concentration information that may unblind the study will not be reported to investigative sites or blinded personnel until the study has been unblinded.

Bioanalytical representatives will be unblinded for PK sample bioanalysis during the conduct of the study. The unblinding of bioanalytical representatives is to be carried out in a secure manner following the sponsor's standard operating procedures. Extreme care and diligence will be taken to ensure no other individuals outside the bioanalytical team will be unblinded.

